7.7. Triggered Requirements

Condition	Action
Neutrophil counts <1000 cells/mm ³	The subject should return to the study site for prompt retesting, ideally within 3-5 days .
Platelet counts <100,000 platelets/mm ³	The subject should return to the study site for prompt retesting, ideally within 3-5 days .
Lymphocyte counts <500 lymphocytes/mm ³	The subject should return to the study site for prompt retesting, ideally within 3-5 days .
Any single AST and/or ALT elevation >3 times the upper limit of normal (ULN)*	The subject should return to the study site for prompt retesting, ideally within 3-5 days .*
Any single hemoglobin value <8.0 g/dL or one that drops ≥2 g/dL below baseline.	The subject should return to the study site for prompt retesting, ideally within 3-5 days .
Any serum creatinine increase >50% over the average of screening (most recent value prior to baseline) and baseline values OR an absolute increase in serum creatinine >0.3 mg/dL (>26.5 μmol/L) over the average of screening (most recent value prior to baseline) and baseline values	The subject should return to the study site for prompt retesting, ideally within 3-5 days . If the second assessment (after the 1 st observations of ≥0.3 mg/dL (or ≥26.5 μmol/L) in serum creatinine relative to subjects' own baseline measurement) is ≥0.4 mg/dL (or ≥35.4 μmol/L), the subject should be discontinued from the study and adequate, immediate, supportive measures taken to correct apparent acute kidney injury.

* The subject must return to the study site for prompt retesting and include the following tests: albumin, creatine kinase (CK), total bilirubin, direct and indirect bilirubin, GGT, PT/INR, and alkaline phosphatase. Additional investigations include a detailed history, occupational exposure, sexual history, travel history, history of contact with a jaundiced subject, surgery, blood transfusion, history of liver or allergic disease, work exposure, history of ethanol, recreational drug and dietary supplement consumption. Testing for acute hepatitis A, B or C infection and biliary tract imaging may be considered. A subject with a total bilirubin value ≥2 × ULN concurrently may need to return to the investigational site and be evaluated as soon as possible, preferably within 48 hours from awareness of the abnormal results (refer to 8.4.2).

090177e190fc2bd0Approved\Approved On: 27-May-2019 05:59 (GMT)

Condition	Action
2 sequential AST or ALT elevations ≥ 3 x ULN with a total bilirubin value ≥ 2 x ULN	Treatment with all study drugs will be discontinued and the subject withdrawn from this study.
2 sequential AST or ALT elevations ≥ 3 x ULN with an elevated INR	Treatment with all study drugs will be discontinued and the subject withdrawn from this study.
2 sequential AST or ALT elevations ≥ 3 x ULN accompanied by symptoms consistent with hepatic injury	Treatment with all study drugs will be discontinued and the subject withdrawn from this study.
2 sequential AST or ALT elevations ≥ 5 x ULN, regardless of Total Bilirubin or accompanying symptoms	Treatment with all study drugs will be discontinued and the subject withdrawn from this study.
Two sequential hemoglobin values < 8.0 g/dL or a decrease of more than 30% from baseline value;	Treatment with all study drugs will be discontinued and the subject withdrawn from this study. Follow up to resolution
Two sequential platelet counts $< 75,000$ platelets/mm ³ ;	Treatment with all study drugs will be discontinued and the subject withdrawn from this study. Follow up to resolution
2 sequential neutrophil counts < 1000 cells/mm ³	Treatment with all study drugs will be discontinued and the subject withdrawn from this study. Follow up to resolution
Confirmed lymphocyte counts < 500 lymphocytes/mm ³ by repeat testing	Treatment with all study drugs will be discontinued and the subject withdrawn from this study. Follow up to resolution
Confirmed increases in serum creatinine $> 50\%$ over the average of screening and baseline values and the absolute value of serum creatinine is above upper limit of normal range.	Treatment with all study drugs will be discontinued and the subject withdrawn from this study. Retesting should occur until the serum creatinine is within 10% of the pretreatment value.
Serious infections defined as any infection (viral, bacterial, or fungal) requiring parenteral antimicrobial therapy or hospitalization for treatment, or meeting other criteria that require the infection to be classified as a serious adverse event.	Treatment with all study drugs will be discontinued and the subject withdrawn from this study
Opportunistic infection judged significant by investigator	Treatment with all study drugs will be discontinued and the subject withdrawn from this study
Malignancies excluding adequately treated non melanoma skin cancer (NMSC) and cervical carcinoma in situ	Treatment with all study drugs will be discontinued and the subject withdrawn from this study
Increase lipid parameters (total cholesterol, LDL cholesterol, HDL cholesterol, triglycerides)	Monitor and treat according to local guidance (eg, diet and behavior modification, statin therapy)

090177e190fc2bd0Approved\Approved On: 27-May-2019 05:59 (GMT)

Condition	Action
Pregnancy or refusal to use appropriate contraception	Permanently withdraw the subject from the study and follow any pregnancy to resolution.
Use of prohibited concomitant medications	See 5.7.2 Concomitant Medications of the protocol for specific actions.
Anaphylactic or other serious allergic reaction	Immediately discontinue study drug and institute appropriate therapy.
Symptoms suggestive of a lupus-like syndrome	Discontinue study drug and institute appropriate therapy
ALT = alanine aminotransferase; AST = aspartate aminotransferase; g/dL = grams per deciliter; GGT = gamma-glutamyl transpeptidase, PT/INR = Prothrombin Time International Normalized Ratio; mm = millimeter; x ULN = times the upper limit of normal	

090177e190fc2bd0\Approved\Approved On: 27-May-2019 05:59 (GMT)

CCI

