6.3. Subject Withdrawal/ Discontinuation Criteria

A subject may withdraw from the study at any time at their own request, or they may be withdrawn at any time at the discretion of the investigator or Pfizer for safety or behavioral reasons, or the inability of the subject to comply with the protocol-required schedule of study visits or procedures at a given study site.

The sponsor's Clinical team should be consulted as soon as possible and subjects should be discontinued if any of the following occur during the study:

- Subjects who have a flare of RA requiring treatment with prohibited concomitant medication should be discontinued.

- Subjects who require rescue doses of acetaminophen/paracetamol or opioid for more than 10 consecutive days for treatment of increased RA symptoms should be discontinued.
- Subjects interrupting study medication for more than 7 consecutive days, or patients who are less than 80% compliant with the dosage regimen for any two consecutive visit periods should be withdrawn from the study.
- Subjects manifesting a serious infection, defined as any infection (viral, bacterial, and fungal) requiring hospitalization or parenteral antimicrobials.
- Any laboratory (defined by changes in serum creatinine or eGFR) or clinical manifestation of acute renal injury (Section 7.6.2 CCI [REDACTED]) [REDACTED]

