9.5. Safety Analyses

All the safety data will be summarized descriptively through appropriate data tabulations, descriptive statistics, and graphical presentations:

- Adverse events will be summarized according to Pfizer standards;
- Serious infections, defined as any infection (viral, bacterial, and fungal) requiring hospitalization or parenteral antimicrobials, will be summarized;
- Any safety events that trigger withdrawal of a subject;
- Safety laboratory tests will be summarized according to Pfizer standards.

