Appendix 6. Guidelines for Monitoring and Discontinuations

The following laboratory abnormalities require re-testing within one week:

- neutrophil counts <1000 neutrophils/ mm^3 ,
- a decrease of hemoglobin <2.0 g/dL from baseline, regardless of baseline value,
- platelet counts $<75,000$ platelets/ mm^3 ,
- an increase in serum creatinine of $>30\%$ AND >0.2 mg/dL from baseline.

Treatment with Tofacitinib will be discontinued and the subject withdrawn from this study for:

- serious infections (those requiring parenteral antimicrobial therapy or hospitalization),
- confirmed neutrophil counts <500 neutrophils / mm^3 ,
- confirmed hemoglobin <7.5 g/dL,
- confirmed platelet counts $<50,000$ platelets/ mm^3 ,
- confirmed AST or ALT elevations >3 X ULN which do not resolve promptly with adjustment of concomitant medications,
- confirmed increase in serum creatinine $>50\%$ over baseline value,
- other serious or severe AEs, after consultation with the Pfizer clinician.

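### Protocol 7.7 defines serious infection more widely than 6.3, 9.5 and Appendix 6, so the 9.5 serious-infection summary can omit an infection for which 7.7 requires withdrawal

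*Protocol*

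**What the plan says.** Four places in the protocol say what a serious infection is.

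- **Section 7.7 (Triggered Requirements)** begins "Serious infections defined as any infection (viral, bacterial, or fungal) requiring parenteral antimicrobial therapy or hospitalization for treatment, or meeting other criteria". Its third limb reads in full "or meeting other criteria that require the infection to be classified as a serious adverse event". The action is "Treatment with all study drugs will be discontinued and the subject withdrawn from this study".
- **Section 6.3 (withdrawal criteria)** introduces its list with "subjects should be discontinued if any of the following occur during the study" and includes "Subjects manifesting a serious infection, defined as any infection (viral, bacterial, and fungal) requiring hospitalization or parenteral antimicrobials". It has no SAE limb.
- **Section 9.5 (Safety Analyses)** plans one grouped summary: "Serious infections, defined as any infection (viral, bacterial, and fungal) requiring hospitalization or parenteral antimicrobials, will be summarized". It has no SAE limb.
- **Appendix 6** lists "serious infections (those requiring parenteral antimicrobial therapy or hospitalization" as a ground for stopping. Its infection item has no SAE limb. The lead-in to that list names tofacitinib only, and the list closes with a general item for other adverse events that are serious or severe, subject to consultation with the sponsor's clinician.

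Section 8.2.3 gives the routes to SAE status. Besides hospitalization they are death, immediate risk of death, lasting or significant disability, congenital anomaly, and an important medical event.

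Section 9.5 also plans a summary of safety events that lead to withdrawal. SAP Section 6.7 summarizes SAEs and withdrawals due to adverse events. The visible SAP text neither defines serious infection nor lists a summary of it.

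**The concern.** One term has two meanings, and the wider one drives withdrawal while the narrower one drives the table. A patient can leave the study under the label of serious infection and be absent from the summary that carries that label. Because the SAP is silent, the narrower wording in 9.5 is the only analysis definition a programmer can see in these documents.

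The summary matters because the trial adds an immunomodulator to methotrexate. Protocol Section 1.7 places serious infection among the important risks of tofacitinib, and SAP Section 3.6 plans one set of safety tables that includes that arm. A grouped count should include every case that the protocol itself calls serious.

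**Working it through.** No sample size, power or event count is involved, so there is no figure to reproduce. The check is to follow one test case through each rule.

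**Test case.** An infection that is an SAE only by a criterion in 8.2.3 other than hospitalization, with no parenteral antimicrobial. Examples are an important medical event treated orally as an outpatient, or a death outside hospital. Prolonging an existing admission does not create such a case, because Section 8.2.4 counts prolongation as hospitalization.

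| Place | Limbs | Outcome for the test case |
|---|---|---|
| 7.7 | parenteral; hospitalization; other SAE criteria | Serious infection; withdrawal required |
| 6.3 | parenteral; hospitalization | Not listed; no trigger here, and no instruction to stay |
| Appendix 6, infection item | parenteral; hospitalization | Outside this item |
| Appendix 6, general item | other serious or severe events | A ground for stopping after consultation; list worded for tofacitinib |
| 9.5, serious-infection summary | parenteral; hospitalization | Not counted |
| 9.5, withdrawal-event summary | any event leading to withdrawal | Counted once the patient is withdrawn under 7.7 |
| SAP 6.7, SAE and AE-withdrawal summaries | all SAEs; all AE withdrawals | Counted |

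**Control case.** An infection needing hospitalization or parenteral antimicrobials counts as serious in all four definitions. The only difference left is that the Appendix 6 list is worded for tofacitinib.

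The definitions therefore diverge only for infections that meet the SAE limb alone. For those, two things differ: the strength of the withdrawal wording (required in 7.7, unlisted in 6.3, after consultation in Appendix 6) and inclusion in the serious-infection summary (not counted under 9.5).

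**The case against.** The strongest reply is that the rules do not collide. A reader might infer that the same patient is withdrawn under one section and kept under another. The documents do not support that. Section 6.3 lists conditions that lead to discontinuation and orders nobody outside the list to continue. It also says of subjects that "they may be withdrawn at any time at the discretion of the investigator or Pfizer for safety or behavioral reasons". Section 7.7 covers the same patient and is mandatory, so a site that applies 7.7 complies with both. This part of the reply stands.

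Appendix 6 is also wider than its infection item suggests, because the general item would catch an infection that is an SAE by another route. That stands too, although it does not close the gap. Stopping after consultation is not the same as required withdrawal. The list also names tofacitinib only, in a double-blind trial where the site does not know who receives it.

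The case also remains visible elsewhere, in the 9.5 withdrawal-event summary and the SAP's SAE and AE-withdrawal summaries. This stands, and it limits the harm to one grouped line.

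A reader might further infer bias in the primary endpoint: one site withdraws the patient, whose Week 12 SDAI is then set to baseline under Protocol 9.2, while another site keeps the patient and observes the score. That needs the same conflict between sections, which is not in the text. No effect on SDAI is shown.

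Finally, a sponsor may deliberately use a narrower definition for analysis than for patient management. Nothing in the visible text says that this was intended, and both places use the same term without qualification.

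**Conclusion.** The concern holds in a limited form. The definition in 7.7 is wider than those in 6.3, 9.5 and the infection item of Appendix 6. Followed as written, 9.5 produces a serious-infection summary that can omit an infection 7.7 calls serious and for which it requires withdrawal. The withdrawal wording also differs in strength between sections and needs reconciling.

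The effect is small. It concerns infections that are SAEs with neither hospitalization nor parenteral antimicrobials, and there may be none. The documents give no infection rate, so no count or percentage is offered.

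The conclusion assumes that the 9.5 line is programmed as written and that no other definition applies from a source not seen here, such as redacted text, the sponsor's reporting standards, or the Safety Review Plan, which SAP Section 3.6.1 says holds the tier-1 event list.

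**What to change.** Define the serious-infection summary in Protocol 9.5 as every infection meeting any limb printed in 7.7: parenteral antimicrobials, hospitalization for treatment, or SAE classification by another criterion. Put the same definition in SAP Section 6.7. Every patient withdrawn for serious infection then appears in the table of that name. Showing the limbs separately would be informative but is optional.

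Separately, the sponsor must reconcile the withdrawal wording in 6.3, 7.7 and Appendix 6, including the tofacitinib-only lead-in of Appendix 6. The reporting fix does not depend on how that is settled, and no withdrawal rule is proposed here.

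The cost is a wording change in the two documents and a slightly wider derivation. Protocol Section 8.1 already requires every SAE to be recorded on the CRF, so the added limb needs no new data. The sponsor should check that antimicrobial route is captured. Protocol Section 5.7 lists indication, daily dose and dates for concomitant medication but not route, and the parenteral limb needs it under either definition. The downside is that the reported serious-infection count may be slightly higher.

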7.9. Investigator Site RA Rater Qualifications

Tender and swollen joint counts will be evaluated by an independent blinded assessor designated at the clinic for the joint count assessment. The independent blinded assessor will only perform the joint counts and will not participate in any other aspect of subject care or data gathering.

For consistency, the same assessor should perform all evaluations across the study for an individual subject when possible. It is especially important that the same assessor evaluate the subject at Screening, baseline, and Week 12 to ensure integrity of the eligibility criteria and the ACR clinical response up to the Week 12 primary endpoint. If the assigned independent blinded assessor cannot be present, the joint counts should be performed by a different blinded assessor. The identity of the independent blinded assessor should be recorded in the source document for each visit.

The independent blinded assessor must have a background in performing RA or other rheumatology clinical trials (eg, systemic lupus erythematosus) involving swollen and tender joint assessment and to have personal prior experience performing joint assessments.

8. ADVERSE EVENT REPORTING

8.1. Requirements

The table below summarizes the requirements for recording safety events on the CRF and for reporting safety events on the Clinical Trial (CT) Serious Adverse Event (SAE) Report Form to Pfizer Safety. These requirements are delineated for 3 types of events: (1) SAEs; (2) non-serious adverse events (AEs); and (3) exposure to the investigational product under study during pregnancy or breastfeeding, and occupational exposure.

Safety Event	Recorded on the CRF	Reported on the CT SAE Report Form to Pfizer Safety Within 24 Hours of Awareness
SAE	All	All
Non-serious AE	All	None
Exposure to the investigational product under study during pregnancy or breastfeeding, and occupational exposure	All (regardless of whether associated with an AE), except occupational exposure	Exposure during pregnancy, exposure via breastfeeding, occupational exposure (regardless of whether associated with an AE)

All observed or volunteered events regardless of treatment group or suspected causal relationship to the investigational product(s) will be reported as described in the following paragraphs.

Events listed in the table above that require reporting to Pfizer Safety on the CT SAE Report Form within 24 hours of awareness of the event by the investigator **are to be reported regardless of whether the event is determined by the investigator to be related to an investigational product under study**. In particular, if the SAE is fatal or life-threatening, notification to Pfizer Safety must be made immediately, irrespective of the extent of available event information. This time frame also applies to additional new (follow-up) information on previously forwarded reports. In the rare situation that the investigator does not become immediately aware of the occurrence of an event, the investigator must report the event within 24 hours after learning of it and document the time of his/her first awareness of the event.

For each event, the investigator must pursue and obtain adequate information both to determine the outcome and to assess whether it meets the criteria for classification as an SAE (see the [Serious Adverse Events](#) section below). In addition, the investigator may be requested by Pfizer Safety to obtain specific follow-up information in an expedited fashion. This information is more detailed than that recorded on the CRF. In general, this will include a description of the event in sufficient detail to allow for a complete medical assessment of the case and independent determination of possible causality. Any information relevant to the event, such as concomitant medications and illnesses, must be provided. In the case of a subject death, a summary of available autopsy findings must be submitted as soon as possible

to Pfizer Safety. Any pertinent additional information must be reported on the CT SAE Report Form; additional source documents (eg, medical records, CRF, laboratory data) are to be sent to Pfizer Safety **ONLY** upon request.

As part of ongoing safety reviews conducted by the sponsor, any non-serious AE that is determined by the sponsor to be serious will be reported by the sponsor as an SAE. To assist in the determination of case seriousness, further information may be requested from the investigator to provide clarity and understanding of the event in the context of the clinical study.

8.1.1. Additional Details On Recording Adverse Events on the CRF

All events detailed in the table above will be recorded on the AE page(s) of the CRF. It should be noted that the CT SAE Report Form for reporting of SAE information is not the same as the AE page of the CRF. When the same data are collected, the forms must be completed in a consistent manner. AEs should be recorded using concise medical terminology and the same AE term should be used on both the CRF and the CT SAE Report Form for reporting of SAE information.

8.1.2. Eliciting Adverse Event Information

The investigator is to record on the CRF all directly observed AEs and all AEs spontaneously reported by the study subject. In addition, each study subject will be questioned about the occurrence of AEs in a non-leading manner.

8.1.3. Withdrawal From the Study Due to Adverse Events (see Also the [Subject Withdrawal Section](#))

Withdrawal due to AEs should be distinguished from withdrawal due to other causes, according to the definition of AE noted below, and recorded on the CRF.

When a subject withdraws from the study because of an SAE, the SAE must be recorded on the CRF and reported, as appropriate, on the CT SAE Report Form, in accordance with the [Requirements](#) section above.

8.1.4. Time Period for Collecting AE/SAE Information

The time period for actively eliciting and collecting AEs and SAEs (“active collection period”) for each subject begins from the time the subject provides informed consent, which is obtained before the subject’s participation in the study (ie, before undergoing any study-related procedure and/or receiving investigational product), through and including a minimum of 28 calendar days after the last administration of the investigational product.

For subjects who are screen failures, the active collection period ends when screen failure status is determined.

